8.3.3 Causality Collection

The investigator should assess causal relationship between IP and each AE, and answer 'yes' or 'no' to the question 'Do you consider that there is a reasonable possibility that the event may have been caused by the investigational product?'

For SAEs, causal relationship should also be assessed for other medication and study procedures. Note: For SAEs that could be associated with any study procedure, the causal relationship is implied as 'yes'.

A guide to the interpretation of the causality question is found in Appendix B.

8.3.4 Adverse Events Based on Signs and Symptoms

All AEs spontaneously reported by the participant or care provider, or reported in response to the open question from the study site staff 'Have you had any health problems since the previous visit/you were last asked?', or revealed by observation, will be collected and recorded in the eCRF. When collecting AEs, the recording of diagnoses is preferred (when possible) to recording a list of signs and symptoms. However, if a diagnosis is known and there are other signs or symptoms that are not generally part of the diagnosis, the diagnosis and each sign or symptom will be recorded separately.

8.3.5 Adverse Events Based on Examinations and Tests

The results from the CSP-mandated laboratory tests and vital signs will be summarized in the Clinical Study Report (CSR). Deterioration as compared to baseline in CSP-mandated laboratory values, vital signs, ECGs, and clinical/neurological assessment(s) should therefore only be reported as AEs if they fulfil any of the SAE criteria, are the reason for discontinuation of treatment with the IP, or are considered to be clinically relevant as judged by the investigator (which may include, but not be limited to, consideration as to whether treatment or non-planned visits were required or other action was taken with the study intervention, e.g., dose adjustment or drug interruption).

If deterioration in a laboratory value/vital sign is associated with clinical signs and symptoms, the sign or symptom will be reported as an AE and the associated laboratory result/vital sign will be considered as additional information. Wherever possible, the reporting investigator uses the clinical, rather than the laboratory term (e.g., anemia versus low hemoglobin value). In the absence of clinical signs or symptoms, clinically relevant deteriorations in non-mandated parameters should be reported as AE(s).

Deterioration of a laboratory value, which is unequivocally due to disease progression, should not be reported as an AE/SAE.

Any new or aggravated clinically relevant abnormal medical finding at a physical examination, as compared with the baseline assessment, will be reported as an AE unless unequivocally related to the disease under study (DUS).

8.3.6 Hy's Law

Cases where a participant shows elevations in liver biochemistry may require further evaluation, and occurrences of AST or ALT $\geq 3 \times$ ULN together with TBL $\geq 2 \times$ ULN may need to be reported as SAEs. Please refer to Appendix E for further instruction on cases of increases in liver biochemistry and evaluation of HL.

8.3.7 Disease Progression

Disease progression can be considered as a worsening of a participant's condition attributable to the disease for which the IP is being studied. It may be an increase in the severity of the DUS and/or increases in the symptoms of the disease. The development of new, or progression of existing metastasis to the primary cancer under study, should be considered as disease progression and not an AE. Events, which are unequivocally due to disease progression, should not be reported as an AE during the study.

8.3.8 Disease Under Study

Symptoms of DUS are those which might be expected to occur as a direct result of SCLC. Events that are unequivocally due to DUS should not be reported as an AE during the study unless they meet SAE criteria or lead to discontinuation of the IP.

8.3.9 Reporting of Serious Adverse Events

All SAEs have to be reported, whether or not considered causally related to the IP or to the study procedure(s). All SAEs will be recorded in the eCRF.

If any SAE occurs in the course of the study, investigators or other site personnel will inform the appropriate AstraZeneca representatives within one day, ie, immediately, but **no later than 24 hours** of when he or she becomes aware of it.

The designated AstraZeneca representative will work with the investigator to ensure that all the necessary information is provided to the AstraZeneca Patient Safety data entry site **within one calendar day** of initial receipt for fatal and life-threatening events **and within 5 calendar days** of initial receipt for all other SAEs.

For fatal or life-threatening AEs where important or relevant information is missing, active follow-up will be undertaken immediately. Investigators or other site personnel will inform AstraZeneca representatives of any follow-up information on a previously reported SAE within one calendar day, ie, immediately, but **no later than 24 hours** of when he or she becomes aware of it.

Once the investigators or other site personnel indicate an AE is serious in the electronic data capture (EDC) system, an automated email alert is sent to the designated AstraZeneca representative.

If the EDC system is not available, then the investigator or other study site staff reports a SAE to the appropriate AstraZeneca representative by telephone.

The AstraZeneca representative will advise the investigator/study site staff how to proceed.

The reference document for definition of expectedness is the IB for AZD2811, the IB for durvalumab, and the local labels for etoposide, carboplatin, cisplatin, and G-CSF.

8.3.10 Pregnancy

All pregnancies and outcomes of pregnancy should be reported to AstraZeneca, except for:

- If the pregnancy is discovered before the study participant has received any study intervention

8.3.10.1 Maternal Exposure

If a participant becomes pregnant during the course of the study, study intervention should be discontinued immediately.

Pregnancy itself is not regarded as an AE unless there is a suspicion that the IP under study may have interfered with the effectiveness of a contraceptive medication. Congenital abnormalities/birth defects and spontaneous miscarriages should be reported and handled as SAEs. Elective abortions without complications should not be handled as AEs. The outcome of all pregnancies (spontaneous miscarriage, elective termination, ectopic pregnancy, normal birth, or congenital anomaly) should be followed up and documented even if the participant was discontinued from the study.

If any pregnancy occurs in the course of the study, then the investigator or other site personnel informs the appropriate AstraZeneca representatives within **1 day**, ie, immediately, but **no later than 24 hours** of when he or she becomes aware of it.

The designated AstraZeneca representative works with the investigator to ensure that all relevant information is provided to the AstraZeneca Patient Safety data entry site **within 1 or 5 calendar days** for SAEs (see Section 8.3.9) and **within 30 days** for all other pregnancies.

The same timelines apply when outcome information is available.

When the eCRF module is used, include the following: The PREGREP module in the eCRF is used to report the pregnancy and the paper-based PREGOUT module is used to report the outcome of the pregnancy.

8.3.10.2 Paternal Exposure

Male participants should refrain from fathering a child or donating sperm during the study and for 9 months after the last dose of AZD2811 and/or durvalumab, whichever is the longer time period. Please follow the local prescribing information relating to contraception.

Pregnancy of the participant's partner is not considered to be an AE. However, the outcome of all pregnancies (spontaneous miscarriage, elective termination, ectopic pregnancy, normal birth, or congenital anomaly) occurring from the date of the first dose until 90 days after the last dose of study intervention should, if possible, be followed up and documented.

Where a report of pregnancy is received, prior to obtaining information about the pregnancy, the investigator must obtain the consent of the participant's partner. Therefore, the local study team should adopt the generic ICF template in line with local procedures and submit it to the relevant Ethics Committees/Institutional Review Boards prior to use.

Participants who are permanently discontinued from further receipt of study intervention, regardless of the reason, will be identified as having permanently discontinued treatment and will enter follow-up (see the SoAs [Table 4]).

8.3.11 Medication Error

If a medication error occurs in the course of the study, then the investigator or other site personnel informs the appropriate AstraZeneca representatives within **1 day**, ie, immediately, but **no later than 24 hours** of when he or she becomes aware of it.

The designated AstraZeneca representative works with the investigator to ensure that all relevant information is completed within **1** (Initial Fatal/Life-Threatening or follow-up Fatal/Life-Threatening) **or 5** (other serious initial and follow-up) **calendar days** if there is an SAE associated with the medication error (see Section 8.3.9) and **within 30 days** for all other medication errors.

The definition of a Medication Error can be found in Appendix B 4.

8.3.12 Adverse Events of Special Interest

An AESI is one of scientific and medical interest specific to an understanding of the study intervention and may require close monitoring. An AESI may be serious or nonserious. The rapid reporting of AESIs allows ongoing surveillance of these events in order to characterize and understand them in association with the use of this study intervention.

8.3.12.1 AESIs for AZD2811

There are no AESIs currently identified for AZD2811.

8.3.12.2 AESIs for Durvalumab

Adverse events of special interest for durvalumab include, but are not limited to, events with a potential inflammatory or immune-mediated mechanism and which may require more frequent monitoring and/or interventions such as steroids, immunosuppressants, and/or hormone replacement therapy. These AESIs are being closely monitored in clinical studies

with durvalumab monotherapy and combination therapy. An imAE is defined as an AESI that is associated with drug exposure and is consistent with an immune-mediated mechanism of action and where there is no clear alternate etiology. Serologic, immunologic, and histologic (biopsy) data, as appropriate, should be used to support an imAE diagnosis. Appropriate efforts should be made to rule out neoplastic, infectious, metabolic, toxin, or other etiologic causes of the imAE.

If the investigator has any questions with regard to an event being an imAE, the investigator should promptly contact the Study Physician.

Adverse events of special interest/imAEs observed with anti-PD-L/PD-1 agents, such as durvalumab, include pneumonitis, hepatitis, diarrhea/colitis, intestinal perforation, endocrinopathies (hypo- and hyper-thyroidism, adrenal insufficiency, hypophysitis/hypopituitarism, and Type 1 diabetes mellitus), nephritis, rash/dermatitis, myocarditis, myositis/polymyositis, pancreatitis, and rare/less frequent imAEs, including neuromuscular toxicities, such as myasthenia gravis, and Guillain-Barre syndrome.

Other inflammatory responses that are rare/less frequent with a potential immune-mediated etiology include, but are not limited to, pericarditis, sarcoidosis, uveitis, and other events involving the eye, skin, hematological, rheumatological events, vasculitis, non-infectious meningitis, and non-infectious encephalitis. It is possible that events with an inflammatory or immune-mediated mechanism could occur in nearly all organs.

In addition, infusion-related reactions and hypersensitivity/anaphylactic reactions with a different underlying pharmacological etiology are also considered AESIs.

Further information on these risks (e.g., presenting symptoms) can be found in the current version of the durvalumab IB. More specific guidelines for their evaluation and treatment are described in detail in the Dose Modification and Toxicity Management Guidelines (see Section 8.5.2). These guidelines have been prepared by the Sponsor to assist the investigator in the exercise of his/her clinical judgment in treating these types of toxicities. These guidelines apply to AEs considered causally related to the study drug/study regimen by the reporting investigator.

8.4 Overdose

For guidance, refer to AstraZeneca standard operating procedure: Reporting of Individual Safety Events in Clinical Studies.

For this study, any dose of study intervention greater than the doses shown in Table 12 and Table 11 (or reduced, as indicated in Table 21 and Table 22), given CC1 will be considered an overdose.

- An overdose with associated AEs is recorded as the AE diagnosis/symptoms on the relevant AE modules in the eCRF and on the Overdose eCRF module
- An overdose without associated symptoms is only reported on the Overdose eCRF module

If an overdose on an AstraZeneca study intervention occurs in the course of the study, the investigator or other site personnel inform appropriate AstraZeneca representatives immediately, but **no later than 24 hours** of when he or she becomes aware of it.

The designated AstraZeneca representative works with the investigator to ensure that all relevant information is provided to the AstraZeneca Patient Safety data entry site **within 1 or 5 calendar days** for overdoses associated with an SAE (see section 8.3.9) and **within 30 days** for all other overdoses.

8.5 Management of Study Intervention-related Toxicities

The following general guidance should be followed for management of toxicities.

- Treat each of the toxicities with maximum supportive care (including holding the agent suspected of causing the toxicity, if required).
- If the symptoms promptly resolve with supportive care, consideration should be given to continuing the same dose of the assigned study intervention along with appropriate continuing supportive care. If medically appropriate, dose modifications are permitted.
- All dose modifications should be documented with clear reasoning and the approach taken.
- During the maintenance phase, if a participant needs to discontinue one of the study interventions, they may continue on study taking only the other study intervention.

All toxicities will be graded according to NCI CTCAE Version 5.0.

8.5.1 Specific Toxicity Management and Dose Modification Information – AZD2811

Substantial acute toxicities should be managed as medically indicated and with temporary suspension of AZD2811, as appropriate. Dose reductions and/or holds are allowed as clinically indicated by the treating physician, according to Table 21 and Table 22. AZD2811 dosing should be delayed if there is any suspicion that a participant is suffering from an infection. In addition, there are certain circumstances in which AZD2811 should be permanently discontinued (Section 7.1).

Dose reductions of AZD2811 should be considered if the toxicity is considered to be related to AZD2811. Dose re-escalation for individual participants is permitted on a case-by-case basis following discussion between the Study Physician and the investigator.

In general, if a participant experiences a Grade 1 or Grade 2 non-hematologic toxicity, no dose modification is required (except dose modifications for skin toxicities in Table 22). If a participant experiences a clinically significant and/or unacceptable toxicity not attributable to the disease or disease-related processes under investigation, dosing will be interrupted, or the dose reduced, and supportive therapy administered as suggested by the treating physician.

If the toxicity resolves or reverts to NCI CTCAE \leq Grade 1 or baseline within 14 days of onset and the participant is showing clinical benefit, treatment with AZD2811 may be restarted using the rules below for dose modifications (see Table 21) and with discussion and agreement with the Study Physician as needed.

If any toxicity does not resolve to NCI CTCAE \leq Grade 1 or baseline after 14 days (Day 35 of the cycle), then the participant should be withdrawn from AZD2811 treatment and observed until resolution of the toxicity (see Table 21). Any participant who develops a Grade 3 or 4 non-hematologic toxicity that does not resolve to \leq Grade 1 or baseline within 14 days should be removed from AZD2811 treatment unless approved by the Study Physician to continue treatment.

In the event of dose delays, the visit cycles will be calibrated such that Day 1 of each cycle is the date that the participant receives the dose.

Table 21 Dose Modification for Non-skin Toxicity

NCI CTCAE v5.0 Toxicity Grade	Action
For all toxicities leading to a dose hold, discontinue AZD2811 treatment if the toxicity does not resolve to NCI CTCAE \leq Grade 1 or baseline after 14 days (ie, by Day 35 of a cycle), with exceptions noted below.	
Non-Hematologic Toxicity	
Grade 3 non-hematologic toxicity lasts > 4 but ≤ 7 days and resolves to \leq Grade 1 or baseline	
 At first occurrence, consider restarting at the same dose If second occurrence (≤ 7 days) Grade 3, reduce to dose level -1 If third time: Reduce to dose level -2 and discuss risk-benefit analysis with Study Physician
Toxicity remains Grade 3 > 7 days (despite supportive therapy)	
 At first occurrence, reduce one dose level If second occurrence, reduce to dose level -2 and discuss risk-benefit analysis with Study Physician
Grade 4 non-hematologic toxicity lasts > 4 but ≤ 7 days and resolves to \leq Grade 1 or baseline	
 At first occurrence, reduce to dose level -1 If second time: Discuss with Study Physician whether risk-benefit analysis supports continuation
Grade 4 non-hematologic toxicity lasts > 7 days	Discuss with Study Physician whether risk-benefit analysis supports continuation
Grade 3 or 4 non-hematologic toxicity that does not resolve to \leq Grade 1 or baseline within 14 days	Discontinue study treatment unless approved by the Study Physician to continue
Sepsis, or any other Grade 3 or 4 non-hematological toxicity, not expected to be manageable/reversible with dose reduction	Discontinue study drug
Hematologic Toxicity	
Participants can only be dosed with AZD2811 on Day 1 of any Cycle if the ANC is $\geq 1.5 \times 10^9/L$ and the platelet count is $\geq 75 \times 10^9/L$.	
Grade 0-3 (except as noted below)	Maintain dose
Grade 2-3 ANC; or Grade 2-3 thrombocytopenia without bleeding or requirement for platelet transfusion	
 Hold until recovery and then maintain dose
Grade 3 thrombocytopenia with bleeding or requiring a platelet transfusion; or Grade 4 ANC	
 First occurrence: Hold until recovery and then reduce to dose level -1 Second occurrence: Dose reduce to level -2 and discuss with Study Physician whether risk-benefit analysis supports continuation

Table 21 Dose Modification for Non-skin Toxicity

NCI CTCAE v5.0 Toxicity Grade	Action
Febrile neutropenia; or Grade 4 thrombocytopenia	
First occurrence: Hold until recovery and then reduce to dose level -2Second occurrence: Discontinue treatment

ANC = absolute neutrophil count; NCI CTCAE = National Cancer Institute Common Terminology Criteria for Adverse Events.

Skin Toxicity

Special attention should be paid to skin observation in participants having skin alterations in their medical history.

Participants will be monitored for appearance of pruritus and/or any signs of rash, including erythematous rash, exfoliative rash, maculo-papular rash, and skin exfoliation throughout study treatment. Participants experiencing skin toxicity should have the following dose modifications applied (see Table 22).

Table 22 Dose Modification for Skin Toxicity

Toxicity	Occurrence	Action
Grade 1: Painless erythema, mild or localized pruritus, rash/acne intervention not indicated, rash/desquamation macular or papular eruption, or erythema without associated symptoms.	Any occurrence	Institute supportive measures, such as topical therapy for symptomatic relief, and continue therapy.
Grade 2: Painful erythema, intense or widespread pruritus, rash/acne intervention indicated, rash/desquamation macular or papular eruption with pruritus or other associated symptoms; localized desquamation or other lesions covering < 50% of BSA. Superficial ulceration < 2 cm; local wound care; medical intervention indicated.	Any occurrence	Institute supportive measures, such as topical therapy for symptomatic relief. Dose reduction or dose hold at the investigator's discretion. Participants requiring > 2 dose reductions will discontinue AZD2811.
Grade \geq 3: Erythema with desquamation, pruritus intense or widespread interfering with ADL, rash/acne associated with pain requiring narcotic analgesics, ulceration or desquamation, rash/desquamation severe generalized erythroderma or macular or popular or vesicular eruption; desquamation covering \geq 50% of BSA. Superficial ulceration \geq 2 cm; local wound care; medical intervention indicated.	Any occurrence	Institute supportive measures, such as topical therapy for symptomatic relief, and interrupt AZD2811 until toxicity has resolved to Grade \leq 1. When resuming treatment after a dose interruption, if obtained within 3 weeks, reduce AZD2811 by one dose level. If toxicity has not returned to Grade \leq 1 in 3 weeks, treatment cannot be resumed without approval of the Sponsor. Participants requiring > 2 dose reductions will discontinue AZD2811.

ADL = activities of daily living; BSA = body surface area.

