4.1.2.2.1 Results of the Safety Run-In

Treatment in the maintenance phase of the trial began in June 2021 and the SRC completed an initial assessment of the safety run-in cohort in September 2021. While no DLTs were experienced by the first six participants, one participant experienced an SAE of neutropenic sepsis with a fatal outcome and one participant experienced an SAE of febrile neutropenia with a fatal outcome during the second cycle of AZD2811 treatment (ie, CCI [REDACTED] Both SAEs were attributed to AZD2811 treatment by the investigators. Additional information about these events and the identified risk of sepsis has been added to the Investigator's Brochure.

Treatment with AZD2811, of new participants entering the maintenance phase, was put on hold while additional data analyses were conducted, and the following protocol amendments were proposed to ensure the safety of current and future participants:

- Maximum AZD2811 dose permitted will be CCI [REDACTED]; maintenance phase eligibility criteria must be confirmed prior to dosing the first cycle of AZD2811
- AZD2811 must not be administered if there is any suspicion of disease progression. Every effort should be made to schedule tumour evaluation scans within 1 week prior

to dosing with AZD2811; scan results **MUST be reviewed** prior to dosing to confirm the absence of disease progression.

- AZD2811 must not be administered if there is any suspicion of infection; consider (prophylactic) antibiotics for participants experiencing Grade 4 ANC or at a high risk of infection. If infection is suspected, work up should be performed to identify whether there is an infection.
- AZD2811 dose will be reduced if a patient experiences Grade 4 ANC, irrespective of time to recovery
- An additional safety visit on Day 12 of [CC1] has been introduced to identify low ANC earlier in the cycle (from Phase I experience, the nadir is expected between 10 to 15 days after AZD2811 dosing).

After implementation of the above recommendations in CSP v8.0, an additional safety run-in cohort will be assessed by the SRC according to Section 4.1.2.2.

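### Table 21's action for a first Grade 4 ANC is a fixed level, so it does not lower the dose of a participant already at level -1 for another toxicity

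*Protocol*

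**What the plan says.** Table 16 (Section 6.6.1) gives three AZD2811 dose levels: 1, -1 and -2. The milligram values are redacted, but only the labels matter here.

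In Table 21 (Section 8.5.1), Grade 4 ANC shares a row with Grade 3 thrombocytopenia complicated by bleeding or transfusion. The two actions in that row are "First occurrence: Hold until recovery and then reduce to dose level -1" and "Second occurrence: Dose reduce to level -2 and discuss with Study Physician whether risk-benefit analysis supports continuation".

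Section 4.1.2.2.1 reports two fatal events in the second AZD2811 cycle, one of neutropenic sepsis and one of febrile neutropenia. It adds: "Both SAEs were attributed to AZD2811 treatment by the investigators". Among the measures then proposed is: "AZD2811 dose will be reduced if a patient experiences Grade 4 ANC, irrespective of time to recovery". It is not limited to participants at the starting dose.

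Other entries take a participant to a lower level for different reasons. Some use relative wording, as for Grade 3 non-hematologic toxicity beyond 7 days: "At first occurrence, reduce one dose level".

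**The concern.** The Grade 4 ANC row counts occurrences of its own toxicities and assigns a fixed level to each count. It does not look at the level the participant is on. If a different toxicity has already brought the participant to -1, the first-occurrence action names the current level, and following the row means restarting at the same dose after severe neutropenia. Section 4.1.2.2.1 says the dose will come down in that situation. The two statements agree for a participant at the starting dose and disagree for one at -1.

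At stake is whether a safety measure adopted after two treatment-attributed deaths is a written requirement for every participant or, for some, is left to the clinician.

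**Working it through.** No sample size, error rate or event figure is involved. The check traces the rule from each dose level.

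**Can a participant be below the starting level before a first Grade 4 ANC?** Yes.

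- To -1, by Table 21: a first Grade 3 non-hematologic toxicity beyond 7 days ("At first occurrence, reduce one dose level"); a second Grade 3 episode of more than 4 and up to 7 days ("Grade 3, reduce to dose level -1"); a first Grade 4 non-hematologic episode of the same duration ("At first occurrence, reduce to dose level -1").
- To -1, by Table 22: Grade 3 or worse skin toxicity, one level down on resuming; Grade 2 skin toxicity at the investigator's discretion ("Institute supportive measures, such as topical therapy for symptomatic relief. Dose reduction or dose hold").
- To -2, by Table 21: a first febrile neutropenia or Grade 4 thrombocytopenia.

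**What does the row do at a first Grade 4 ANC?**

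| Level before | Literal result | Dose lowered, as Section 4.1.2.2.1 says? |
|---|---|---|
| 1 | -1 | Yes |
| -1 | -1 | No |
| -2 | Stays at -2 | No lower level exists |

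The entry at -2 needs care. The row names a level above the current dose, but Section 8.5.1 allows re-escalation only case by case after discussion between the Study Physician and the investigator, so the row cannot by itself raise the dose. What is missing is a required discussion before restarting at -2.

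**Does other text close the gap at -1?** Sections 6.6.1, 7.1, 8.5 and 8.5.1 permit clinically indicated reductions or stopping, and bring in the Study Physician on restart as needed. Section 8.5.1 says reductions should be considered for AZD2811-related toxicity. None of these makes a further reduction mandatory, and the Section 8.5.1 permission refers back to Tables 21 and 22. Table 21's opening line requires AZD2811 to stop if a toxicity that led to a hold has not resolved after 14 days. That covers slow recovery, whereas Section 4.1.2.2.1 requires a reduction however quickly the count recovers.

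**With a relative action:** 1 goes to -1 (as now), -1 goes to -2, and -2 goes to Study Physician discussion. The second-occurrence entry still works: it already requires that discussion, whatever the level.

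**Exposure.** Section 9.4 gives 9 patients on the combination. If the two fatal cases are among them (an assumption), 9 - 2 = 7 remain as the upper limit.

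**The case against.** The case against giving this weight is substantial.

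- **Intent is clear.** Both the row and Section 4.1.2.2.1 say the dose is reduced, and a careful physician would probably go to -2. This stands, but it describes likely practice and not what the row requires.
- **Status of the text.** Section 4.1.2.2.1 lists proposed amendments. Version 8.0 was not implemented, and its text is kept in version 9.0 for reference. The urgent measures went out in a Dear Investigator Letter that is not among the documents, so what sites were told about Grade 4 ANC is unknown. This stands and lowers the practical weight. Table 21 is still the printed rule in the current protocol.
- **Counting within the row.** If the earlier event was complicated Grade 3 thrombocytopenia, a Grade 4 ANC may count as the second occurrence and lead to -2. The row does not say. The point therefore rests on toxicities from other rows or Table 22.
- **Other safeguards.** A second Grade 4 ANC leads to -2 with discussion, and an unresolved hold leads to discontinuation. Both stand; neither covers a first Grade 4 ANC at -1 that recovers promptly.

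A reader might infer that this gap is connected with the two deaths. The documents do not support that. Sepsis and febrile neutropenia have their own stricter rows (discontinue; and straight to -2, then discontinue). The events preceded the proposed measures, and nothing says either participant had been held at -1.

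A reader might also extend the point to the two non-hematologic entries that name level -1. The wording is the same, but Section 4.1.2.2.1 makes no commitment about those toxicities. Nor do the documents call for a stop rule across Table 21: Table 22's rule of stopping when more than two reductions are needed sits in the skin rows only.

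**Conclusion.** The point holds for one action in one row. For a participant already at -1 through another row or Table 22, the first-occurrence action for Grade 4 ANC, read literally, leaves the dose unchanged and does not meet Section 4.1.2.2.1. At -2 the remaining gap is only that restarting needs no discussion.

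Severity is minor. Harm would need a participant still on AZD2811, already at -1 for a different toxicity, who then has a first Grade 4 ANC and whose clinician does not go lower. At most 9 participants were exposed and new starts are barred. Enrolled patients could continue, and Section 4.4 allows treatment after the data cut-off with sponsor approval. It would go beyond the documents to say that anyone is now at risk, since they do not state whether any participant remains on AZD2811. No endpoint or analysis is affected.

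The conclusion assumes that occurrences are counted within a row, since no text pools them across rows.

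**What to change.** In the row for Grade 4 ANC or complicated Grade 3 thrombocytopenia, change only the first-occurrence action: hold until recovery, then restart one level below the current dose; if the participant is already at -2, the Study Physician is consulted on whether benefit and risk justify going on. The relative wording is already used elsewhere in Table 21 and in Table 22. The non-hematologic entries and the rest of the table can stay as they are, or be aligned if the sponsor prefers.

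The clinical cost is that some participants reach level -2 sooner. The administrative cost is one changed action in one table, with no new visits, data or patients. Appendix A 1 requires ethics and regulatory approval for an amendment, so the sponsor should first check whether anyone is still receiving AZD2811. If no one is, no action is needed.
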